#### **2.9.1 Adverse events (AEs)**

For adverse events and other binary safety variables, crude incidence and exposure time-adjusted incidence will be derived as described below and summarized in [Table 2-11](#).

Only treatment emergent adverse events will be summarized. However all AEs will be included in the listing with flags for treatment emergent. If needed a separate AE listing can be provided to display exclusively AEs with start date later than 84 days since last dose and until EOS.

Treatment emergent adverse events are defined as events started on or after the first dose of study medication or events present prior to the first dose of study medication but increased in severity after dosing based on preferred term and within last dose + 84 days.

**Table 2-11      Overview of analyses on some safety endpoints**

| Analysis Period                    | AEs & important risks                                | SAEs & important risks                               | AES-SMQ  | AEs by severity   | study treatment related AEs, death & other significant AEs | Notable (lab/vitals/ECG) |
|------------------------------------|--|--|--|-------------------|--|--------------------------|
| Induction Period (Day 1 -Week 12)  | • crude incidence                                    | • crude Incidence                                    | • crude incidence                                    | • crude incidence | • crude Incidence  | • crude incidence        |
| Maintenance Period (up to week 52) | • crude incidence                                    | • crude Incidence                                    | • crude incidence                                    | • crude incidence | • crude Incidence  |                          |
| Entire treatment                   | • crude incidence
• exp. time adjusted Incidence* | • crude incidence
• exp. time adjusted Incidence* | • crude Incidence
• exp. time adjusted Incidence* | • crude incidence | • crude Incidence
• exp. time adjusted Incidence*       | • crude Incidence        |
| Entire study                       | • exp. time adjusted Incidence*                      | • exp. time adjusted Incidence*                      |  |                   |  |                          |

\*Note: exposure adjusted incidence rates will be provided and follow the guideline as below:

- Primary SOC level for AE and SAE
- Level 1 for risks and SMQ
- PT level for SAE
- PT level for AE  $\geq 4\%$ , or events that had an incidence rate of at least 5.0 cases per 100 subject-years in one of any treatment group
- Other selected AEs on lower levels (e.g. PT or SMQ level 2), if **appropriate**

**Exposure adjusted incidence rates will be also provided for the entire treatment period, by the following subgroups:**

- Treatment emergent AEs by SOC, PT and by age strata
- Treatment emergent AEs by SOC, PT and by body weight strata
- Treatment emergent SAEs by SOC, PT and by age strata
- Treatment emergent SAEs by SOC, PT and by body weight strata
- Important identified and potential risks (level 1) based on all adverse events by age strata
- Important identified and potential risks (level 1) based on all adverse events by body weight strata

The crude incidence of treatment emergent adverse events will be summarized by primary system organ class and preferred term. Confidence intervals for the crude rate will be derived as described in [Section 5.1](#). In addition, exposure time-adjusted rates (incidence rate) including 95% confidence intervals may be provided.

AEs and serious AEs will be summarized by presenting, for each treatment group (including any AIN457), the number and percentage of subjects having any AE, having an AE in each primary system organ class and having each individual AE (preferred term). Summaries (crude incidences only) will also be presented for AEs by severity. If a particular AE 'severity' is missing, then this variable will be listed as missing and treated as missing in summaries. If a subject reported more than one adverse event with the same preferred term, then the adverse event with the greatest severity will be presented. If a subject reported more than one adverse event within the same primary system organ class, then the subject will be counted only once with the greatest severity at the system organ class level, where applicable.

AEs and SAEs will be presented in terms of exposure time-adjusted incidence rates with 95% confidence intervals for entire study period (up to EOS).

Adverse events will also be summarized by standardized or customized MedDRA queries (SMQ or CMQ/NMQ). The MedDRA version used for reporting the adverse events will be described in a footnote.

The most common adverse events reported ( $\geq z\%$  in any group for each preferred term in the table by SOC and PT or  $\geq z\%$  in any group for each grouping term table) will be presented in descending frequency according to its incidence in secukinumab group starting from the most common event. Here, the threshold value  $z$  is set to 4 (%) but it may be updated following review of the dry run outputs.

Separate summaries will be provided for deaths and serious adverse events, other significant adverse events leading to discontinuation and adverse events leading to dose adjustment or interruption.

For SAEs that occurred during screening, a listing will be prepared for all subjects screened including screening failures.

For the adverse events that occurred after the treatment errors those subjects who received erroneously the wrong treatment at least once, will be listed.

### **Clinicaltrials.gov and EudraCT**

For the legal requirements of ClinicalTrials.gov and EudraCT, two required tables on treatment emergent adverse events which are not serious adverse events with an incidence greater than X% and on treatment emergent serious adverse events and SAE suspected to be related to study treatment will be provided by system organ class and preferred term on the safety set population. Here, the threshold value X is set to 2-5 (%) but it may be updated following review of the dry run outputs.

If for a same patient, several consecutive AEs (irrespective of study treatment causality, seriousness and severity) occurred with the same SOC and PT:

- a single occurrence will be counted if there is  $\leq 1$  day gap between the end date of the preceding AE and the start date of the consecutive AE

- more than one occurrence will be counted if there is > 1 day gap between the end date of the preceding AE and the start date of the consecutive AE

For occurrence, the presence of at least one SAE / SAE suspected to be related to study treatment / non SAE will be checked in a block e.g., among AE's in a  $\leq$  1 day gap block, if at least one SAE is occurring, then one occurrence is calculated for that SAE.

### **Important identified and potential risks**

Other safety topics of interest, such as risks defined in the Safety Profiling Plan, Risk Management Plan or topics of interest regarding signal detection or routine analysis are defined in the Program Case Retrieval Sheet [REDACTED]

Crude rate of important identified and potential risks from Case Retrieval Sheet will be provided for all (non-serious and serious) cases and for all serious cases. Exposure-time adjusted rates will be provided for treatment period including all data for all (non-serious and serious) cases and for all serious cases. The summary tables for serious cases will not be provided in case of small number of patients.

Risk measures and confidence intervals will be derived according to [Section 5](#).

The version of the Case Retrieval Sheet used for the analyses will be described in a footnote. This includes MedDRA version and Novartis MedDRA Query (NMQ) dictionary date.

**Important note:** For the evaluation of risks primary and secondary system organ classes of the MedDRA dictionary will be considered.

### **Analyses by IRT dosing error**

Additional analysis will be performed for the treatment emergent adverse events on or after Week 13 visit and up to Day 365, by IRT dosing error, by primary system organ class and preferred term. See [Section 4.1](#) for details.

Adverse events that occurred from Week 13 up to Day 365 since randomization for subjects affected by IRT dosing error will be listed.

#### **2.9.2 Deaths**

Separate summary and listing will be provided for deaths.

#### **2.9.3 Laboratory data**

The summary of laboratory evaluations will be presented for three groups of laboratory tests (hematology, clinical chemistry and urinalysis). All laboratory data will be listed with "on-treatment" flag displayed.

For urinalysis, frequency tables will be presented.

The general guideline for laboratory summaries (hematology and clinical chemistry) is as below:

- All the summary of lab outputs (newly occurring or worsening notables, maximum changes, shift tables, by visit summary statistics) will consider the "on-treatment" data. i.e., all assessments within last dose plus 84 days.

Descriptive summary statistics for the change from baseline to each study visit will be presented. These descriptive summaries will be presented by laboratory test and treatment group. Change from baseline will only be summarized for subjects with both baseline and post baseline values and will be calculated as:

$$\text{change from baseline} = \text{post baseline value} - \text{baseline value}$$

The laboratory test values below the Lower Level of Quantification (LLQ) or above the Upper Level of Quantification (ULQ) will be imputed as LLQ or ULQ values, respectively. The numerical part of the reported result will be treated as the actual LLQ or ULQ. These laboratory values will be displayed in listings using the standard unit with the reported sign (“<” or “>”).

In addition, shift tables will be provided for all parameters to compare a subject's baseline laboratory evaluation relative to the most extreme laboratory test value within a treatment period. For the shift tables, the normal laboratory ranges will be used to evaluate whether a particular laboratory test value is normal, low, or high (including category “high and low”). These summaries will be presented by laboratory test and treatment group. Subjects with abnormal laboratory values will be listed and values outside the normal ranges will be flagged.

The following laboratory parameters will be analyzed with respect to numerical Common Terminology Criteria for Adverse Events (CTCAE) grades, given [Table 2-13](#): hemoglobin, platelets, white blood cell count, neutrophils, lymphocytes, creatinine, total bilirubin (TBL), gamma-glutamyl transferase (GGT), alanine aminotransferase (ALT), aspartate aminotransferase (AST), alkaline phosphatase (ALP), estimated glomerular filtration rate (eGFR).

**Table 2-13 CTCAE grades for laboratory parameters to be analyzed**

| CTCAE v4.0 Term                   | Grade 1              | Grade 2               | Grade 3               | Grade 4  |
|-----------------------------------|----------------------|-----------------------|-----------------------|--|
| HGB decreased (Anemia)            | <LLN - 100 g/L       | <100 - 80 g/L         | <80 g/L               | Life-threatening consequences; urgent intervention indicated |
| Platelet count decreased          | <LLN - 75.0 x10e9 /L | <75.0 - 50.0 x10e9 /L | <50.0 - 25.0 x10e9 /L | <25.0 x 10e9 /L  |
| White blood cell decreased        | <LLN - 3.0 x 10e9 /L | <3.0 - 2.0 x 10e9 /L  | <2.0 - 1.0 x 10e9 /L  | <1.0 x 10e9 /L   |
| Neutrophil count decreased        | <LLN - 1.5 x 10e9 /L | <1.5 - 1.0 x 10e9 /L  | <1.0 - 0.5 x 10e9 /L  | <0.5 x 10e9 /L   |
| Lymphocyte count decreased        | <LLN - 0.8 x 10e9 /L | <0.8 - 0.5 x 10e9 /L  | <0.5 - 0.2 x 10e9 /L  | <0.2 x 10e9 /L   |
| Creatinine increased              | >ULN - 1.5 x ULN     | >1.5 - 3.0 x ULN      | >3.0 - 6.0 x ULN      | >6.0 x ULN   |
| TBL increased                     | >ULN - 1.5 x ULN     | >1.5 - 3.0 x ULN      | >3.0 - 10.0 x ULN     | >10.0 x ULN  |
| GGT increased                     | >ULN - 2.5 x ULN     | >2.5 - 5.0 x ULN      | >5.0 - 20.0 x ULN     | >20.0 x ULN  |
| ALT increased                     | >ULN - 3.0 x ULN     | >3.0 - 5.0 x ULN      | >5.0 - 20.0 x ULN     | >20.0 x ULN  |
| AST increased                     | >ULN - 3.0 x ULN     | >3.0 - 5.0 x ULN      | >5.0 - 20.0 x ULN     | >20.0 x ULN  |
| ALP increased                     | >ULN - 2.5 x ULN     | >2.5 - 5.0 x ULN      | >5.0 - 20.0 x ULN     | >20.0 x ULN  |
| Glucose increased (Hyperglycemia) | >ULN - 8.9 mmol/L    | >8.9 - 13.9 mmol/L    | >13.9 - 27.8 mmol/L   | >27.8 mmol/L   |
| Glucose decreased (Hypoglycemia)  | <LLN - 3.0 mmol/L    | <3.0 - 2.2 mmol/L     | <2.2 - 1.7 mmol/L     | <1.7 mmol/L  |

| eGFR | <LLN-60
ml/min/1.73m  | <60-30
ml/min/1.73m  | <30-15
ml/min/1.73m  | <15
ml/min/1.73m  |
|------|--------------------------------------|-------------------------------------|-------------------------------------|----------------------------------|
|------|--------------------------------------|-------------------------------------|-------------------------------------|----------------------------------|

Note: Per protocol fasting glucose was only required based on glucose urine dipstick result, therefore due to low occurrences it will only be listed and not tabulated.

The number and percentage of subjects with clinically CTCAE grade newly occurring or worsening after baseline (treatment emergent) will be presented. Analysis of hematology CTCAE grades will also be presented by age strata and by body weight strata. Shift tables will be presented comparing baseline laboratory result (CTCAE grade) with the worst results (expressed in CTCAE grade) during the treatment phase analyzed. A panel group will be provided to display shift of baseline to minimum evaluation based on CTCAE grades for each hematology parameter (including Leukocytes, neutrophils, lymphocytes and platelets).

### 2.9.3.1 Liver events

Summaries generated will include:

- Criterion-based “event” tables for selected liver function tests: newly occurring or worsening liver enzyme abnormalities based on the event criteria given in [Table 2-14](#).
- Standard laboratory change from baseline tables of liver function test which are generated by visit. The laboratory tests are listed in [Table 2-14](#).

Listing generated will include overview of liver events; laboratory values of patients with liver events; viral serology, autoimmunity, imaging, pathology, drug abuse of patients with liver events.

For a combined criterion to be fulfilled, all conditions have to be fulfilled on the same visit. The criteria are not mutually exclusive, e.g., a subject with ALT = 6.42xULN is counted for ALT >3xULN and ALT >5x ULN.

**Table 2-14 Liver-related events**

| Parameter              | Criterion  |
|------------------------|--|
| ALT                    | >ULN; >3xULN; >5xULN; >8xULN; >10xULN  |
| AST                    | >ULN; >3xULN; >5xULN; >8xULN; >10xULN  |
| ALT or AST             | >3xULN; >5xULN; >8xULN; >10xULN  |
| TBL                    | >ULN; >1.5xULN, >2xULN   |
| ALP                    | >ULN; >1.5xULN, >2xULN, >3xULN, >5xULN   |
| ALT or AST & TBL & INR | ALT or AST >3xULN & TBL >1.5xULN;
ALT or AST >3xULN & TBL >2xULN;
ALT or AST >5xULN & TBL >2xULN;
ALT or AST >8xULN & TBL >2xULN
ALT or AST >10xULN & TBL >2xULN
ALT or AST > 3x ULN & INR > 1.5          |
| ALT or AST & TBL & ALP | ALP > 3x ULN & TBL > 2x ULN
ALP > 5x ULN & TBL > 2x ULN
ALT or AST >3xULN & TBL >2xULN & ALP <2xULN ( Potential Hy's Law )
(ALT or AST > 3x ULN & TBL > 2x ULN & ALP < 2x ULN) or reported Hy's Law case |

---

ALT or AST > 3x ULN & (nausea or vomiting or fatigue or general malaise or abdominal pain or (rash and eosinophilia))

---

Liver event will be listed based on ALT and ALP measurements using the closest lab assessment +/- 7 days from the onset of these liver event into the following characteristics ‘Hepatocellular’ (ALT > 2xULN or ALT/ULN:ALP/ULN > 5), ‘Cholestatic’ (ALP > 2xULN or ALT/ULN:ALP/ULN ≤ 2), ‘Mixed’ (ALT > 2xULN and ALP > ULN and 2 < ALT/ULN:ALP/ULN ≤ 5), ‘None’ (if none of the three above qualifies), and ‘Unknown’ (in case of a missing ALT or ALP values). Note that the categories are not mutually exclusive.

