## 14 Appendix 2: Liver event and Laboratory trigger Definitions and Follow-up Requirements

**Table 14-1 Liver Event and Laboratory Trigger Definitions**

Definition/ threshold	
LIVER LABORATORY TRIGGERS	
 
• <math>3 \times \text{ULN} < \text{ALT} / \text{AST} \leq 5 \times \text{ULN}</math>
 
• <math>1.5 \times \text{ULN} < \text{TBL} \leq 2 \times \text{ULN}</math>
 

LIVER EVENTS	
 
• ALT or AST <math>> 5 \times \text{ULN}</math>
 
• ALP <math>> 2 \times \text{ULN}</math> (in the absence of known bone pathology)
 
• TBL <math>> 2 \times \text{ULN}</math> (in the absence of known Gilbert syndrome)
 
• ALT or AST <math>> 3 \times \text{ULN}</math> and INR <math>> 1.5</math>
 
• Potential Hy's Law cases (defined as ALT or AST <math>> 3 \times \text{ULN}</math> and TBL <math>> 2 \times \text{ULN}</math> [mainly conjugated fraction] without notable increase in ALP to <math>> 2 \times \text{ULN}</math>)
 
• Any clinical event of jaundice (or equivalent term)
 
• ALT or AST <math>> 3 \times \text{ULN}</math> accompanied by (general) malaise, fatigue, abdominal pain, nausea, or vomiting, or rash with eosinophilia
 
• Any adverse event potentially indicative of a liver toxicity *
 

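### SAP 2.9.3.1: the liver-pattern rule lists normal ALT and ALP as 'Cholestatic' whenever their ratio is 2 or less, and makes every 'Mixed' event also 'Hepatocellular'

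*SAP*

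**What the plan says.** The text below Table 2-14 in SAP 2.9.3.1 assigns each liver event a pattern from ALT and ALP, "using the closest lab assessment +/- 7 days from the onset of these liver event". With R for the ratio (ALT/ULN)/(ALP/ULN), the classes are:

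- The cholestatic class is defined as "ALP > 2xULN or ALT/ULN:ALP/ULN ≤ 2".
- The hepatocellular class has the same form: either ALT exceeds twice ULN or R exceeds 5.
- The mixed class needs three things together: ALT above twice ULN, ALP above ULN, and R greater than 2 but no more than 5.
- 'None' is left for events that meet no other rule, and 'Unknown' for events where ALT or ALP is missing.

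The SAP adds: "Note that the categories are not mutually exclusive". The pattern is used in a listing only.

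The SAP gives no liver event definition of its own, so I take the one in Protocol Appendix 2, Table 14-1. That table has eight definitions. Three need no raised enzyme: total bilirubin above 2xULN, an adverse event suggesting liver toxicity, and "Any clinical event of jaundice (or equivalent term)".

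**The concern.** A pattern label should tell the reader which enzyme dominates once at least one is raised. Two features of the printed logic prevent this.

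- In the first two rules the ratio is joined to the enzyme limit by 'or'. The ratio can then assign a pattern by itself, at any absolute level. A ratio of two normal values says nothing about the type of liver injury.
- 'Mixed' is built from a condition that is already sufficient for 'Hepatocellular', so the two labels do not separate.

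At stake is how individual liver events are read in a paediatric trial with a dedicated liver-monitoring procedure (Protocol 7.3). A child with jaundice or an isolated bilirubin rise and normal ALT and ALP could be listed with a cholestatic pattern that the laboratory data do not show.

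**Working it through.** The plan gives no figure to reproduce here, so the check applies the printed rules literally. ALT and ALP are in multiples of ULN.

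**1. Single cases**

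| ALT | ALP | R | Label(s) as printed |
|---|---|---|---|
| 1.0 | 1.0 | 1.00 | Cholestatic |
| 0.5 | 0.5 | 1.00 | Cholestatic |
| 0.8 | 0.6 | 1.33 | Cholestatic |
| 0.9 | 0.4 | 2.25 | None |
| 3.0 | 0.9 | 3.33 | Hepatocellular |
| 3.0 | 1.2 | 2.50 | Hepatocellular and Mixed |
| 3.0 | 1.6 | 1.88 | Hepatocellular and Cholestatic |
| 6.0 | 2.5 | 2.40 | Hepatocellular, Cholestatic and Mixed |

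The first three rows have no raised enzyme and are still 'Cholestatic'. The fourth shows that this happens only when R is 2 or less.

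**2. Share of normal pairs labelled 'Cholestatic'**

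The documents give no distribution, so this rests on an assumption: ALT and ALP independent and uniform on [a, 1] xULN. With neither enzyme above 2xULN, the label applies exactly when R ≤ 2. For a ≤ 0.5, the area where ALT > 2·ALP is the integral of (1 − 2p) from p = a to 0.5, which is (0.5 − a)². Hence

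share = 1 − (0.5 − a)² / (1 − a)²

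| a | Calculation | Share | Check on a 0.01-step grid |
|---|---|---|---|
| 0.1 | 1 − 0.16/0.81 | 80.2% | 80.2% |
| 0.2 | 1 − 0.09/0.64 | 85.9% | 85.8% |
| 0.3 | 1 − 0.04/0.49 | 91.8% | 91.7% |
| 0.4 | 1 − 0.01/0.36 | 97.2% | 97.0% |
| 0.5 | 1 − 0/0.25 | 100% | 100% |

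Unequal ranges give a figure in the same band. For ALT on 0.2 to 1.0 and ALP on 0.3 to 1.0, the share is 1 − 0.04/0.56 = 92.9%.

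On the widest grid (a = 0.1), a further 3.3% of normal pairs are 'Hepatocellular' through R > 5. The same 'or' causes this.

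**3. 'Mixed' against 'Hepatocellular'**

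'Mixed' requires ALT > 2xULN. ALT > 2xULN is sufficient for 'Hepatocellular'. So 'Mixed' is a subset of 'Hepatocellular' by construction. On a grid of ALT and ALP from 0.1 to 12xULN in steps of 0.1, all 1,995 'Mixed' points are also 'Hepatocellular', and 1,530 of them are 'Cholestatic' as well.

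**4. Is replacing 'or' by 'and' enough?**

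No. It turns every normal pair into 'None' and removes the double labels, but ALT 3x with ALP 1.6x then also becomes 'None' although ALT is raised. The rule needs restructuring.

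**The case against.** The strongest reply is that little depends on this label. It appears in one listing and is neither counted nor tested. Laboratory values of patients with liver events are listed too, so a reader can see that the enzymes are normal. ALT, AST, bilirubin and ALP are each tabulated singly in Table 2-14. The SAP discloses the overlap. Five of the eight definitions in Protocol Table 14-1 require a raised ALT, AST or ALP, so events with both ALT and ALP normal come from a minority of definitions. The uniform ranges are not in the documents.

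Most of this stands, and it limits the size of the point. It does not remove the defect. Disclosing overlap neither explains a class wholly contained in another nor justifies a cholestatic label on normal enzymes. Also, the definitions written as ALT or AST can be met on AST alone, with ALT normal.

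Three stronger readings are tempting and are not supported.

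- *The rule for combined criteria misses cases.* SAP 2.9.3.1 says: "For a combined criterion to be fulfilled, all conditions have to be fulfilled on the same visit". A reader might infer an error, because ALT 4.2x on Day 85 and bilirubin 2.4x on Day 113 would not be counted together. But the rule is stated openly, and the protocol joins the components without any time window. ALT, AST, bilirubin and ALP come from one chemistry panel (Protocol 6.5.5.2). INR is outside that panel, but event follow-up lists it with ALT and AST (Protocol Table 14-2). For the symptom criterion, adverse events carry dates rather than visits, so an operational definition is missing. That is a gap in detail, not a shown error.
- *'None' can hardly be reached.* ALT 0.9x with ALP 0.4x reaches it.
- *80% to 100% of liver events will be mislabelled.* The figure describes assumed normal pairs, not the events that enter the listing.

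**Conclusion.** The point holds for the pattern labels. Followed exactly, the SAP lists a liver event with normal ALT and ALP as 'Cholestatic' whenever R ≤ 2, and lists every 'Mixed' event as 'Hepatocellular' too. Both follow from the printed logic and need no distributional assumption. That normal pairs reach the rule rests on the liver event definition in Protocol Table 14-1.

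The 80% to 100% range rests on independent, uniform normal-range values and only shows that the label is the usual outcome for such pairs. The number of patients affected cannot be derived from the documents. The consequence is limited to reading one descriptive listing: no efficacy test, error rate, sample size or protocol action for a patient depends on the label.

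**What to change.** Replace the pattern rules below Table 2-14 with the following sequence, which keeps the SAP's own cut-offs:

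1. ALT or ALP missing: 'Unknown'.
2. Neither ALT nor ALP above 2xULN: 'None'.
3. ALT above 2xULN and ALP not above ULN: 'Hepatocellular'.
4. Otherwise by ratio: R > 5 'Hepatocellular'; 2 < R ≤ 5 'Mixed'; R ≤ 2 'Cholestatic'.

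The steps are taken in order and the three ratio intervals cover all values, so each event gets exactly one label. In the examples above, ALT 1x/ALP 1x becomes 'None', 3x/0.9x stays 'Hepatocellular', 3x/1.2x and 6x/2.5x become 'Mixed', and 3x/1.6x becomes 'Cholestatic'. The last assignment should be confirmed with the medical team, because ALT is the more raised enzyme there. Whatever is chosen, that cell must be defined.

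Delete the note on non-exclusive categories for the patterns. Keep the separate statement in 2.9.3.1 that the threshold criteria overlap, which is correct for counts such as ALT above 3x and above 5xULN. The same-visit rule needs no change on this account.

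The cost is a few lines of SAP text and re-programming one listing. No new data are needed.
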